### **9.3.1 Informed Consent Form and Explanatory Material**

In Japan, the principal investigator will prepare the consent form and explanatory material required to obtain subject's consent to participate in the study with the cooperation of the sponsor and will revise these documents as required. The prepared or revised consent forms and explanatory material will be submitted to the sponsor. Approval of the IRB will be obtained prior to use in the study.

### **9.3.2 Revision of the Consent Form and Explanatory Material**

In Japan, when important new information related to the subject's consent becomes available, the principal investigator will revise the consent form and explanatory material based on the information without delay and will obtain the approval of the IRB prior to use in the study. The investigator will provide the information, without delay, to each subject already participating in the study, and will confirm the intention of each subject to continue the study or not. The investigator shall also provide a further explanation using the revised form and explanatory material and shall obtain written consent from each subject of their own free will to continue participating in the study.

## **10.0 Source Documents and Case Report Form Completion**

### **10.1 Source Documents**

Source documents are defined as original documents, data and records. This may include hospital records, clinical and office charts, laboratory data/information, subjects' diaries or evaluation checklists, pharmacy dispensing and other records, recorded data from automated instruments, microfiches, photographic negatives, microfilm or magnetic media, and/or x-rays. Data collected during this study must be recorded on the appropriate source documents. The Investigator Awareness Date (SAE eCRF) may serve as the source for this data point. This AE data point required for eCRF completion can be entered directly in the eCRF.

The investigator(s)/institution(s) will permit study-related monitoring, audits, IEC/IRB review, and regulatory inspection(s), providing direct access to source data documents.

During the COVID-19 or any pandemic, remote monitoring of data may be employed if allowed by the local regulatory authority, IRB/IEC, and the study site.

### **10.2 Electronic Case Report Forms (eCRF)**

eCRFs must be completed for each subject screened/enrolled in this study. These forms will be used to transmit information collected during the study to AbbVie and regulatory authorities, as applicable. The CRF data for this study are being collected with an EDC system called Rave® provided by the technology vendor Medidata Solutions Incorporated, NY, USA. The EDC system and the study-specific eCRFs will comply with Title 21 CFR Part 11. The documentation related to the validation of the EDC system is available through the vendor, Medidata, while the validation of the study-specific eCRFs will be conducted by AbbVie and will be maintained in the Trial Master File at AbbVie.

The investigator will document subject data in his/her own subject files. These subject files will serve as source data for the study. All eCRF data required by this protocol will

be recorded by investigative site personnel in the EDC system. All data entered into the eCRF will be supported by source documentation.

The investigator or an authorized member of the investigator's staff will make any necessary corrections to the eCRF. All change information, including the date and person performing the corrections, will be available via the audit trail, which is part of the EDC system. For any correction, a reason for the alteration will be provided. The eCRFs will be reviewed periodically for completeness, legibility, and acceptability by AbbVie personnel (or their representatives). AbbVie (or their representatives) will also be allowed access to all source documents pertinent to the study in order to verify eCRF entries. The principal investigator will review the eCRFs for completeness and accuracy and provide his or her electronic signature and date to eCRFs as evidence thereof.

Medidata will provide access to the EDC system for the duration of the trial through a password-protected method of internet access. Such access will be removed from investigator sites at the end of the site's participation in the study. Data from the EDC system will be archived on appropriate data media (CD-ROM, etc.) and provided to the investigator at that time as a durable record of the site's eCRF data. It will be possible for the investigator to make paper printouts from that media.

### **10.3 Electronic Patient Reported Outcomes (ePRO)**

Patient reported data must be completed for each subject screened/enrolled in this study. Some of these data are being collected with an Electronic Patient Reported Outcome (ePRO) system called Trialmax, provided by the technology vendor CRF Health of Plymouth Meeting, PA, USA. The ePRO system is in compliance with Title 21 CFR Part 11. The documentation related to the system validation of the ePRO system is available through the vendor, CRF Health, while the user acceptance testing of the study specific PRO design will be conducted and maintained at AbbVie.

The subject will be entering the data on two electronic devices; these data will be uploaded to a server. The data on the server will be considered source, and maintained and managed by CRF Health.

Internet access to the ePRO data will be provided by CRF Health for the duration of the study. This access will be available for the duration of the study to the site investigator, as well as delegated personnel. Such access will be removed from investigator sites following the receipt of the study archive. Data from the ePRO system will be archived on appropriate data media (CD-ROM, etc.) and provided to the investigator at that time as a durable record of the site's ePRO data. It will be possible for the investigator to make paper print-outs from that media.

The ePRO data will be collected by the following methods:

#### **Diary Based**

The ePRO data (number of total and liquid or very soft stools, stool consistency per Bristol Stool Chart, use of medications used for endoscopy preparation, if an endoscopy was performed, AP, and general well-being) will be collected electronically via a handheld device into which the subject will record the required pieces of information on a daily basis. The electronic device will be programmed to allow data entry once per day.

All data entered on the device will be immediately stored to the device itself and manually/automatically uploaded to a central server administrated by CRF Health. The investigational site staff will be able to access all uploaded subject entered data via a password protected website, up until the generation, receipt and confirmation of the study archive.

#### **Tablet Based**

The ePRO data (IBDQ, CSS, EQ-5D-5L, WPAI-CD, SF-36, FACIT-F, PGI-S, and PGIC) will be collected electronically via an onsite device at visits specified in [Appendix C](#). The electronic device will be programmed to allow data entry once per day per study subject.

All data entered on the device will be immediately stored to the device itself and manually/automatically uploaded to a central server administrated by CRF Health. The investigator and delegated staff, will be able to access all uploaded patient entered data via a password protected website, up until the generation, receipt and confirmation of the study archive.

Due to the COVID-19 or any pandemic, subject visits may be conducted via phone or video conference. PROs are eligible for completion by interview at the visits specified in [Appendix C](#). In this situation, sites will read the PRO questions and response options to the subject and record the subject's responses. The subject's ability to view the PRO to understand the questions and response options should be preserved. Sites may share the questionnaire by videoconference or send the questionnaires (email or hard copy) to the subjects to allow them to read/understand the questions and responses when the subject is providing responses over the phone. The date and time of PRO data collection should be recorded along with the name of the person who collected the information.

## **11.0 Data Quality Assurance**

To ensure data integrity and subject safety, a study monitor will, throughout the study, verify that all subjects signed agreement of informed consent prior to any study-specific procedures being conducted. The study monitor will confirm that the investigator is conducting the study in compliance with the protocol, GCP and applicable regulations, and verify that the information reported in the eCRF is complete, accurate, and supported by information in source documents.

Computer logic and manual checks will be created to identify items such as inconsistent study dates. Any necessary corrections will be made to the eCRF.

## **12.0 Use of Information**

All information concerning upadacitinib and AbbVie operations, such as AbbVie patent applications, formulas, manufacturing processes, basic scientific data, or formulation

information, supplied by AbbVie and not previously published is considered confidential information.

The information developed during the conduct of this clinical study is also considered confidential and will be used by AbbVie in connection with the development of upadacitinib. This information may be disclosed as deemed necessary by AbbVie to other clinical investigators, other pharmaceutical companies, and to governmental agencies. To allow for the use of the information derived from this clinical study and to ensure complete and thorough analysis, the investigator is obligated to provide AbbVie with complete test results and all data developed in this study and to provide direct access to source data/documents for study-related monitoring, audits, IEC/IRB review, and regulatory inspection.

This confidential information shall remain the sole property of AbbVie, shall not be disclosed to others without the written consent of AbbVie, and shall not be used except in the performance of this study.

The investigator will maintain a confidential subject identification code list of all subjects enrolled in the study, including each subject's name, subject number, address, phone number and emergency contact information. This list will be maintained at the study site with other study records under adequate security and restricted access, and will not be retrieved by AbbVie.

Any exploratory research that may be done using the samples from this study will be experimental in nature and the results will not be suitable for clinical decision making or patient management. Hence, neither the investigator, the subject, nor the subject's physician (if different from the investigator) will be informed of individual subject results, should analyses be performed, nor will anyone not directly involved in this research. Correspondingly, researchers will have no access to subject identifiers. Individual results will not be reported to anyone not directly involved in this research other than for regulatory purposes. Aggregate data from exploratory research from this study may be used in scientific publications or presented at medical conventions. Exploratory research

data will be published or presented only in a way that does not identify any individual subject.

### **13.0 Completion of the Study**

The investigator will conduct the study in compliance with the protocol and complete the study within the timeframe specified in the contract between the Investigator (Director of the Site in Japan) and AbbVie. Continuation of this study beyond this date must be mutually agreed upon in writing by both the investigator (Director of the Site in Japan) and AbbVie. The investigator will provide a final report to the IEC/IRB following conclusion of the study, and will forward a copy of this report to AbbVie or their representative.

The investigator (Director of the Site in Japan) must submit, maintain, and archive any records related to the study according to ICH GCP and all other applicable regulatory requirements. If the investigator (Director of the Site in Japan) is not able to retain the records, he/she must notify AbbVie to arrange alternative archiving options.

AbbVie will select the signatory investigator from the investigators who participate in the study. Selection criteria for this investigator will include level of participation as well as significant knowledge of the clinical research, investigational drug and study protocol. The signatory investigator for the study will review and sign the final study report in accordance with the European Agency for the Evaluation of Medicinal Products Guidance on Investigator's Signature for Study Reports.

The end-of-study is defined as the date of the last subject's last visit.

## **Appendix A. Responsibilities of the Clinical Investigator**

Clinical research studies sponsored by AbbVie are subject to the Good Clinical Practices (GCP) and local regulations and guidelines governing the study at the site location. In signing the Investigator Agreement in Section 14.0 of this protocol, the investigator is agreeing to the following:

1. Conducting the study in accordance with the relevant, current protocol, making changes in a protocol only after notifying AbbVie, except when necessary to protect the safety, rights or welfare of subjects.
2. Personally conducting or supervising the described investigation(s).
3. Informing all subjects, or persons used as controls, that the drugs are being used for investigational purposes and complying with the requirements relating to informed consent and ethics committees (e.g., independent ethics committee [IEC] or institutional review board [IRB]) review and approval of the protocol and amendments.
4. Reporting adverse experiences that occur in the course of the investigation(s) to AbbVie and the site director.
5. Reading the information in the Investigator's Brochure/safety material provided, including the instructions for use and the potential risks and side effects of the investigational product(s).
6. Informing all associates, colleagues, and employees assisting in the conduct of the study about their obligations in meeting the above commitments.
7. Maintaining adequate and accurate records of the conduct of the study, making those records available for inspection by representatives of AbbVie and/or the appropriate regulatory agency, and retaining all study-related documents until notification from AbbVie.
8. Maintaining records demonstrating that an ethics committee reviewed and approved the initial clinical investigation and all amendments.

9. Reporting promptly, all changes in the research activity and all unanticipated problems involving risks to human subjects or others, to the appropriate individuals (e.g., coordinating investigator, institution director) and/or directly to the ethics committees and AbbVie.
10. Following the protocol and not make any changes in the research without ethics committee approval, except where necessary to eliminate apparent immediate hazards to human subjects.

**Appendix C. Study Activities**

Activity	Part 1 – 12-Week Double-Blind Induction Part 2 – Open-Label Single-Arm Induction						Part 3 – Extended Treatment Period			Premature Discontinuation Visit	Unscheduled Visit b	30-Day Follow-Up Visit
	Screening a	Baseline	Week 2	Week 4	Week 8	Week 12	Week 16	Week 20	Week 24			
Informed Consent	X											
Inclusion/Exclusion c	X	X										
Medical/Surgical History c	X	X										
Prior and Concomitant Medications c,#	X	X	X	X	X	X	X	X	X	X	X	X
Physical Exam d,+ and Vital Signs e,#	X	X	X	X	X	X	X	X	X	X	X	
Endoscopy f,+ and SES-CD	X					X			X	X		
Biopsy g,+	X					X			X	X		
12-Lead ECG h,+	X					X			X	X		
Latent TB Risk Factor Assessment Form	X											
PPD Skin Test or QuantiFERON-TB Gold Test i	X											
Chest X-ray j	X											
FSH k	X											
HBV, HCV and HIV Screening l	X											
HBV Periodic Screening m,+						X			X			

Activity	Part 1 – 12-Week Double-Blind Induction Part 2 – Open-Label Single-Arm Induction						Part 3 – Extended Treatment Period			Premature Discontinuation Visit	Unscheduled Visit b	30-Day Follow-Up Visit
	Screening a	Baseline	Week 2	Week 4	Week 8	Week 12	Week 16	Week 20	Week 24			
C. difficile toxin	X											
Blood Chemistry and Hematology n,o,ab,+	X	X	X	X	X	X	X	X	X	X	X	X
hs-CRP =		X	X	X	X	X	X	X	X	X	X	X
Urinalysis o,p,ab,+	X					X			X	X		
Pregnancy Test q,ab,+	X	X	X	X	X	X	X	X	X	X		X
Upadacitinib Plasma Concentration r,=			X	X	X	X	X	X	X	X		
Stool Sample (FCP) s,=		X		X		X	X		X	X		
Lymphocyte Subsets =		X		X		X	X		X	X		
CDAI =		X t	X	X	X	X	X	X	X	X	X	
Patient Questionnaires: # IBDQ EQ-5D-5L WPAI SF-36 FACIT-F CSS		X		X		X			X	X		
PGI-S #		X	X	X	X	X			X	X	X	
PGIC #			X	X	X	X			X	X	X	
AE Assessment u,#	X	X	X	X	X	X	X	X	X	X	X	X
Study Drug Dispensing/ Administration ab		X		X	X	X v	X	X				

Activity	Part 1 – 12-Week Double-Blind Induction Part 2 – Open-Label Single-Arm Induction						Part 3 – Extended Treatment Period			Premature Discontinuation Visit	Unscheduled Visit b	30-Day Follow-Up Visit
	Screening a	Baseline	Week 2	Week 4	Week 8	Week 12	Week 16	Week 20	Week 24			
Dispense Subject Diary	X											
Subject Diary Review w,#		X	X	X	X	X	X	X	X	X	X	
Optional biologic drug level x,=	X											
Optional Pharmacogenetic y,=		X										
Optional Epigenetic y,=		X		X		X			X	X		
Optional Serum and Plasma y,=		X		X		X			X	X		
Optional mRNA y,=		X		X		X			X	X		
Optional Stool Proteomic y,z,=		X		X		X						
Optional Stool Microbiota y,z,=		X		X		X						
Optional Intestinal Biopsy aa,=	X					X			X	X		

CDAI = Crohn's Disease Activity Index; CSS = Crohn's Symptoms Severity Questionnaire; ECG = electrocardiogram; EQ-5D-5L = European Quality of Life 5 Dimensions 5 Levels; FACIT-F = Functional Assessment of Chronic Illness Therapy-Fatigue; FCP = fecal calprotectin; hs-CRP = high-sensitivity C-reactive protein; IBDQ = Inflammatory Bowel Disease Questionnaire; PGIC = Patient Global Impression of Change; PGI-S = Patient Global Impression of Severity; SES-CD = Simplified Endoscopic Score for Crohn's disease; SF-36 = Short Form-36; PD = premature discontinuation; WPAI = Work Productivity and Activity Impairment Questionnaire

- a. The Screening Period will be a minimum of 8 days but no more than 35 days prior to Baseline Visit. Baseline Visit date will serve as the reference for all subsequent visits. A ± 3-day window is permitted around scheduled study visits.
- b. Visits to retest a lab will not be considered an unscheduled visit. Unscheduled visits according to this table are for purposes when the subject is coming in for a visit for evaluation and assessment.

- c. Update inclusion/exclusion, prior and concomitant therapy, and medical/surgical history information to assure subject eligibility. All subjects need to have their average daily very soft or liquid SF and average daily AP score calculated and meeting eligibility criteria before randomization at Baseline.
- d. Physical examinations are full physical examinations performed at Screening, Baseline, and Week 12; and Week 24/PD if the subject undergoes Part 3. Physical examinations at all other visits are symptom-based but should include an assessment of EIMs and presence or absence of cutaneous fistulas, as part of calculating the CDAI. During the full physical examination, all subjects will be assessed for presence and number of draining and non-draining enterocutaneous (perianal and abdominal) and rectovaginal fistulas at Baseline, Week 12, and Week 24/PD. If the assessment of presence and number of draining and non-draining fistulas were performed during Screening or the visit for endoscopy, this may be used for the respective Baseline, Week 12 or Week 24/PD visits.
- e. Blood pressure, pulse rate, temperature, respiratory rate and weight should be performed before blood draws are performed. Height will be measured at Screening only (with shoes off).
- f. Ileocolonoscopies will be used to calculate the SES-CD. The Screening ileocolonoscopy should be done during the Screening Period or within 45 days of the Baseline Visit, if video recorded. Endoscopic evaluations using SES-CD confirmed by central reader will be done at Screening. Patients who complete at least 8 weeks in Part 1 and Part 2 or at least 20 weeks in Part 3 will be required to have an endoscopy. Where COVID-19 or any pandemic affects Week 12 or Week 24 endoscopy, a  $\pm$  7-day window is permitted.
- g. Biopsy may be done when performing the endoscopy. At Screening, biopsy to confirm CD diagnosis must be done when performing the endoscopy if appropriate documentation for confirmation of the diagnosis does not exist. Biopsies to rule out dysplasia and colon cancer may be taken at the investigator's discretion. Optional intestinal biopsy samples for histopathology and biological investigations, including but not limited to, transcriptomic analyses and immunohistochemistry may be evaluated in approximately 200 subjects (intestinal biopsy substudy).
- h. Subjects with normal ECG within 90 days of Screening would not require a repeat ECG, if documentation is available. Subjects can have a repeat ECG at any time during the study as warranted based on the opinion of the investigator.
- i. PPD skin test is to be read 48 to 72 hours after placement. Subjects with negative QuantiFERON TB Gold test and/or PPD test within 90 days of Screening will not require a repeat test (documentation must be available). In case of positive PPD/positive or repeat indeterminate IGRA testing, in the absence of active TB, the subject may participate in the study after initiation of latent TB treatment (regimen according to local practice/guidelines).
- j. Chest x-ray includes posterior-anterior view and lateral view. Subjects can have a chest x-ray anytime during the study as warranted based on the opinion of the investigator. In Japan and China, a CT scan of the chest may be performed in lieu of a chest x-ray, at the investigator's discretion.
- k. FSH should be tested at Screening if the female subject is  $\leq$  55 years of age AND has had no menses  $\geq$  12 months AND has no history of permanent surgical sterilization (Refer to Section 5.2.4).
- l. Subjects will be tested for the presence of HBV and HCV at Screening. A positive result for HBs Ag or hepatitis C (HCV RNA detectable in any subject with anti-HCV Ab) will be exclusionary. For subjects who are negative for both HBs Ag and HBs Ab but are positive for HBc Ab, HBV DNA PCR will be performed and any result that meets or exceeds detection sensitivity will be exclusionary. HIV testing will be performed at the central laboratory, unless prohibited by local regulations. The central lab will report the HIV test results directly to the sites. AbbVie will not receive results from the HIV testing and not be made aware of any positive result.

- m. For Japan or countries who mandate periodic screening for HBV: subjects with positive HBs Ab and/or positive HBc Ab and a negative HBV DNA PCR test result at Screening should have HBV DNA PCR test performed at 12 and 24 weeks; in cases where recurrence of HBV DNA is observed, the subject should be discontinued from the study. This measure is not necessary in patients with history of HBV vaccination and positive HBs Ab result.
- n. Laboratory tests performed during the Screening Period can be repeated in case the abnormalities are considered to be transient by the investigator.
- o. Minimum 8-hour fast for chemistry. If a subject is not able to fast, the non-fasting status will be recorded in study source documentation. Urinalysis, chemistry and hematology may be collected at other scheduled and unscheduled visits than indicated in the table in case of repeat test for toxicity management criteria or if they are warranted by the investigator.
- p. Urinalysis will be completed by the central lab at the required visits. A microscopic analysis will be performed in the event the dipstick results show leukocytes, nitrite, protein, ketones, or blood greater than negative or glucose greater than normal.
- q. Serum pregnancy test will be performed on all women of childbearing potential at Screening. Urine pregnancy test will be performed locally at the Baseline Visit prior to the first dose of study drug and at all subsequent visits, including the 30-day follow-up visit for all women of childbearing potential (refer to Section 5.2.4). If any urine pregnancy test is positive, a serum pregnancy test will be performed by the central laboratory. If serum pregnancy test comes back borderline, a repeat test is necessary (pregnancy is an exclusion criterion). If still borderline  $\geq 3$  days later, this will be considered documentation of continued lack of a positive result and the subject can be enrolled into the study in absence of clinical suspicion of pregnancy or other pathological cause of borderline result. If a pregnancy is identified, the pregnancy must be reported to AbbVie.
- r. At the Week 4 visit, PK samples should be collected prior to dosing if possible and the subjects should take the study drug dose at the clinic after collecting the PK blood sample. However, if the subject normally takes the study drug dose at a time that is after the time of the scheduled study visit, the subject should follow the regular dosing schedule and the PK sample should be collected at any time during the visit. At Week 16 and Week 20 visits, PK samples will not be collected from subjects in Part 3 Cohort 3, who received open-label upadacitinib in Part 2. For all other visits, PK samples should be collected at any time during the visit and the subject should follow the regular dosing schedule.
- s. A stool sample will be collected at each time point indicated for FCP. For the visit that endoscopy will be conducted, stool sample should be collected prior to bowel prep. Subjects will be asked to provide a stool sample at the visit, if possible, or the site will give instructions and a stool sample supply kit.
- t. Diary information collected during Screening will serve to calculate Baseline CDAI.
- u. Collection of SAEs begins the day the subject signs the informed consent form.
- v. Only for subjects continuing into Part 3.
- w. Diary review includes a review of ePRO data (number of total and liquid or very soft stools, stool consistency per Bristol Stool Chart ([Appendix F](#)), use of medications used for endoscopy preparation, if an endoscopy was performed, AP, and general well-being).

- x. During Screening, biologic drug levels may be optionally assessed at the investigator's discretion as an alternative to completing the required washout period: (1) infliximab and natalizumab: may be tested approximately 4 weeks from the last dose; (2) adalimumab, certolizumab, golimumab, or vedolizumab: may be tested approximately 6 weeks from the last dose; (3) ustekinumab: may be tested approximately 8 weeks from the last dose.
- y. Only if subject provides written consent to collect the samples; if the informed consent form is not signed, no samples can be collected.
- z. Optional stool samples for proteomic and microbiota analyses may be evaluated in approximately 200 subjects (fecal biomarker substudy).
- aa. If subject provides written consent, intestinal biopsy samples for histology and exploratory analyses will be collected in approximately 200 subjects as a substudy; if the informed consent form is not signed, no intestinal biopsy can be collected. Biopsies will be obtained at Screening and at the Week 12 endoscopy; and at Week 24/PD, if the subject participates in Part 3.
- ab. During the COVID-19 or any pandemic, when a lab test cannot be collected per protocol, the administration and dispensing of study drug should occur if the investigator feels it is safe to continue study drug based on the remote visit, at least one post-Baseline lab test is available and no longer than 6 weeks have passed since the last safety lab tests. A local laboratory can be utilized when it is not feasible to use the central laboratory.
- # Study activity that can be performed by phone/virtually within a  $\pm$  7-day window when an onsite study visit is not possible due to COVID-19 or any pandemic, if allowed by local regulations. This is applicable for all visits, except Screening and Baseline visits, which must be completed at the study site. Physical examination that requires palpation should not be performed. Patient questionnaire EQ-5D-5L is not eligible to be performed by phone/virtually.
- + Study activity that can be performed at a local facility when an onsite study visit is not possible due to COVID-19 or any pandemic, if allowed by local regulations. This is applicable for all visits, except Screening and Baseline visits, which must be completed at the study site.
- = Study activity should not be performed by phone/virtually or at a local facility, when an onsite study visit is not possible due to COVID-19 or any pandemic. Screening and Baseline visit procedures must be completed at the study site.

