### **Hepatitis B**

Subjects will be tested for the presence of HBV at screening using the following tests:

- HBs Ag (Hepatitis B surface antigen)
- HBc Ab/anti-HBc (Hepatitis B core antibody)
- HBs Ab/anti-HBs (Hepatitis B surface antibody)

HBV serologic test results will be interpreted and managed as shown in [Figure 3](#).

A positive result for HBs Ag will be exclusionary.

A negative result for HBs Ag will trigger automatic reflex testing for core antibodies (HBc Ab) and surface antibodies (HBs Ab).

For a subject who has had an HBV vaccination (should document in the medical history), a positive test result for HBs Ab is expected, the HBV DNA PCR qualitative testing is **not** required and the subject may be enrolled (Scenario B).

A negative test result for HBc Ab does **not** require HBV DNA PCR qualitative testing and the subject may be enrolled (Scenarios A and B).

[figure not shown]
A positive test result for HBc Ab requires HBV DNA PCR testing (automatic reflex testing) (Scenarios C and D).

- A positive result for HBV DNA or a result that exceeds detection sensitivity will be exclusionary.

- A subject with a negative result for HBV DNA may be enrolled.

Where mandated by local requirements, subjects with positive HBs Ab and/or positive HBc Ab and a negative HBV DNA PCR test at Screening, should have HBV DNA PCR test performed at every 12 weeks. HBV DNA PCR testing every 12 weeks is not necessary when the subject has a history of HBV vaccine and HBs Ab+. In cases where recurrence of HBV DNA is observed, the subject should be discontinued from the study.

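### Appendix C footnote l sets a narrower trigger for the screening HBV DNA test than Section 5.3.1.1, exclusion criterion 29 and Table 5

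*Protocol*

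**What the plan says.** Protocol Appendix C, footnote l, covers HBV, HCV and HIV screening. After excluding HBs Ag positive subjects, it says: "For subjects who are negative for both HBs Ag and HBs Ab but are positive for HBc Ab, HBV DNA PCR will be performed". It adds that a result at or above detection sensitivity excludes the subject. It gives no other trigger for the screening PCR.

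Protocol Section 5.3.1.1, Hepatitis B, states the rule without reference to HBs Ab: "A positive test result for HBc Ab requires HBV DNA PCR testing (automatic reflex testing"), and assigns it to Scenarios C and D. A negative HBc Ab does not require "HBV DNA PCR qualitative testing and the subject may be enrolled (Scenarios A and B").

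Four other places bear on the point:

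- The note to Figure 3 requires PCR for an HBs Ab positive result in subjects with no vaccination history, and in subjects in Japan.
- Exclusion criterion 29 (Section 5.2.2) defines active HBV by a PCR result in HBc Ab positive subjects, with no HBs Ab condition.
- Table 5 (AST or ALT) has an HBV DNA rule for HBc Ab positive subjects with negative screening DNA, and says explicitly that HBs Ab status does not matter.
- Footnote m, directly below footnote l, speaks of "subjects with positive HBs Ab and/or positive HBc Ab and a negative HBV DNA PCR test result at Screening". It therefore expects a screening DNA result in some HBs Ab positive subjects.

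**The concern.** The PCR separates an HBc Ab positive subject who may be enrolled from one who must be excluded. The study drug is a JAK inhibitor, and the protocol's introduction names viral reactivation among the risks of reduced immune function. The trigger for the test should therefore read the same wherever it appears.

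It does not. A coordinator who takes the trigger from the schedule would find no instruction to test a subject who is HBc Ab positive and HBs Ab positive. If that subject had detectable HBV DNA, criterion 29 would exclude them, but the result needed to apply it would be missing. The HBV DNA rule in Table 5 is worded for subjects whose screening DNA was negative, so an untested subject would fall outside its literal terms. The ALT/AST thresholds for interrupting study drug would still apply, and the investigator could still order the test.

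**Working it through.** The plan gives no figure to reproduce, so the check compares the rules. Take HBs Ag negative subjects, since HBs Ag positive subjects are excluded outright. Classify them by HBc Ab (2) × HBs Ab (2) × vaccinated or not (2) × Japan or not (2) = 16 profiles. These are combinations of the rule, not subjects.

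| HBc Ab | HBs Ab | Unvaccinated or in Japan | Profiles | Footnote l | Section 5.3.1.1 HBc Ab rule | Figure 3 note |
|---|---|---|---|---|---|---|
| + | − | either | 4 | PCR | PCR | – |
| + | + | yes | 3 | – | PCR | PCR |
| + | + | no | 1 | – | PCR | – |
| − | + | yes | 3 | – | – | PCR |
| − | + | no | 1 | – | – | – |
| − | − | either | 4 | – | – | – |

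Profiles sent to PCR:

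- Footnote l: 4 of 16.
- HBc Ab rule of Section 5.3.1.1: 4 + 3 + 1 = 8 of 16.
- HBc Ab rule plus the Figure 3 note: 8 + 3 = 11 of 16.

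What is missed under three ways of working:

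1. **Appendix C alone.** Against the HBc Ab rule, 8 − 4 = 4 profiles are missed. These are all the HBc Ab+/HBs Ab+ profiles, whether vaccinated or not and whether in Japan or not. Against the full requirement, 11 − 4 = 7 are missed. The other 3 are HBc Ab negative profiles that only the Figure 3 note sends to PCR.
2. **Footnote l with the Figure 3 note.** The two do not overlap, because one needs HBs Ab negative and the other HBs Ab positive. Together they cover 4 + 6 = 10, so 11 − 10 = 1 profile is missed: HBc Ab+/HBs Ab+, vaccinated, outside Japan.
3. **Section 5.3.1.1 in full.** 11 − 11 = 0.

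Corrected wording: all HBc Ab positive profiles (8) plus the HBs Ab positive profiles that the Figure 3 note adds (3) = 11 of 11. Simply deleting the HBs Ab condition would give 8 of 11 and leave out the 3 HBc Ab negative profiles.

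One sentence in Section 5.3.1.1 could seem to exempt the profile left over in case 2. It begins "For a subject who has had an HBV vaccination (should document in the medical history), a positive test result for HBs Ab is expected" and goes on to say that no PCR is needed. The sentence is labelled Scenario B, and the same section lists Scenario B under a negative HBc Ab. Read that way, it does not reach HBc Ab positive subjects. The Figure 3 image is not available here, so the content of the scenarios is inferred from these labels.

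**The case against.** The strongest reply is that footnote l is incomplete rather than wrong. It does not say that only these subjects are tested, it waives nothing for HBs Ab positive subjects, and what it says about HBs Ab negative, HBc Ab positive subjects is correct. Section 5.3.1 describes Appendix C as a tabular summary of procedures set out in the text. Section 5.3.1.1 makes the PCR an automatic reflex on a positive HBc Ab, Table 2 lists it as reflex only, and a central laboratory processes the samples. On those terms the test follows from the laboratory result and not from a site reading a footnote. Eligibility is also checked at both Screening and Baseline.

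All of this stands, and it lowers the likely consequence. It does not make the footnote right: a schedule that states an eligibility trigger should not state a narrower one than the criterion it serves.

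A reader might infer two stronger things that the documents do not support. The first is that the exposure is confined to vaccinated subjects outside Japan. That holds only for someone who skips the HBc Ab rule in Section 5.3.1.1 yet applies the Figure 3 note in the same section. The second is that the screening PCR is the sole scheduled HBV DNA test for that group because later testing is waived for them. The waivers exist: "HBV DNA PCR testing every 12 weeks is not necessary when the subject has a history of HBV vaccine and HBs Ab" positive (Section 5.3.1.1), and "This measure is not necessary in patients with history of HBV vaccination and positive HBs Ab result" (footnote m). But periodic testing applies only in Japan or where local rules mandate it. Elsewhere no subject has it scheduled, vaccinated or not, so the waiver does not single this group out.

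**Conclusion.** The point holds as an internal inconsistency in a safety rule. Footnote l is narrower than Section 5.3.1.1, exclusion criterion 29 and Table 5 for HBc Ab positive, HBs Ab positive subjects. The reach depends on the text in use: all four such profiles under Appendix C alone, one if the Figure 3 note is added, none if Section 5.3.1.1 is followed.

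Practical risk is low, provided the laboratory reflex is set up as Section 5.3.1.1 describes. The documents do not show how it was configured. They do not report how many subjects are HBc Ab and HBs Ab positive, and nothing in them indicates that anyone went untested, so it would be wrong to conclude that subjects were missed. Endpoints, analysis sets, type I error, power and sample size are unaffected. The correction is worth making because it concerns an operative eligibility rule and costs very little.

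**What to change.** Reword footnote l along these lines: *HBV DNA PCR will be performed for every HBs Ag negative, HBc Ab positive subject regardless of HBs Ab result, and for HBs Ab positive subjects as specified in Section 5.3.1.1 and Figure 3.* The second clause is needed so that the footnote also matches the Figure 3 note. Section 5.3.1.1, criterion 29 and Table 5 need no change for this point.

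Optionally, run one listing from existing laboratory data to confirm that every enrolled HBc Ab positive subject has a screening HBV DNA result, and test any who do not.

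The cost is one line in the schedule, carried by the next amendment or administrative change, plus the listing if it is run. No new visits or routine samples are needed.
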